Cow milk allergy (CMA) and egg allergies are the most common food allergies in children and recent reports suggest that rates of resolution are considerably lower than previous estimates.⁽¹⁵⁻¹⁷⁾ Further, both CMA and egg allergy are associated with severe anaphylaxis^(18;19) and due their ubiquitous use in our diet are almost impossible to strictly avoid.⁽²⁰⁻²²⁾ In line with these, several studies suggest that quality of life of patients with milk/egg allergy and their families is severely impaired.⁽²³⁻²⁵⁾

With the support of AllerGen NCE and CIHR we have initiated in 2014 the first cross Canada study to assess milk desensitization. This study now includes almost 50 patients,

and our preliminary results reveal an almost 80% success rate . We are now proposing to initiate an egg desensitization study based on the expertises, recruitment skills and data collected in our first 2 years of milk desensitization.

We hypothesize that there will be at least 50% improvement in the ability to tolerate egg. E.g. a child that was able to tolerate only 40 mg of merengue will be able to tolerate at least 60 mg subsequent to desensitization

The trial design is an RCT aiming to demonstrate superiority of the desensitization protocol to an avoidance strategy regarding the tolerated quantity of egg . The ratio of patients to control is 1:1 . Patients will be block randomized in groups of 2 according to age and sex.

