The rising incidence of food allergies is occurring more rapidly than changes to the genome sequence would allow ⁽⁵⁵⁾ and epigenetic regulation (heritable changes in gene expression that occur in the absence of alterations in DNA sequences) may in part mediate the complex gene-by-environment interactions that can lead to asthma. ⁽⁵⁶⁾ Experimental studies provide substantial in vitro data indicating that DNA methylation of genes critical to T-helper cell differentiation may induce polarization toward or away from an allergic phenotype. Methylation of DNA and resulting changes in chromatin structure have been shown to initiate the process by which the Th cells lose their plasticity and differentiate productively toward the Th1 versus the proallergic Th2 pattern

of cytokine gene expression.⁽⁵⁷⁻⁵⁹⁾ So far no studies have explored the role of DNA methylation in short term processes such as desensitization for food allergens.

3.vii. Gaps in role of allergen specific salivary IgA.

We hypothesize that development of an enhanced antigen specific mucosal IgA response is associated with reduced responses to oral antigen challenge in food allergy in children. Antigens delivered to the gastrointestinal mucosa are subject to a variety of barriers before they come into contact with effector cells such as mast cells, loaded with antigen specific IgE, that may trigger an adverse allergic reaction. Since the majority of allergic effector cells within the intestinal tract are below the epithelial barrier, and IgA is in much higher concentration than IgE, we may enhance blockade against allergic reactions in previously sensitized individuals through increases in mucosal IgA, and especially through an increased IgA:IgE ratio. While this has been examined experimentally in mice, the relationship between mucosal IgA and desensitization in the clinical setting is not defined.

4. Methodological Approach/Study Design

Thirty four boys and girls with between 6 to 18 years of age, diagnosed with egg allergy will be approached by our study group. Participants will be recruited from the allergy clinic at the Montreal Children's Hospital.

Inclusion criteria: Children 6 years and older who satisfy all the following criteria will be included:

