Potential participants are referred to the study team by their treating allergist. They are given information about the study and a follow-up conversation - to review the study aims and procedures - with the study coordinator is scheduled. Typically, families of the potential participants will be given a week to review the study information. Following this, if potential participants are still interested in participating, they will meet with one of the investigators to review the potential benefits and risks of participation

It has been our experience that with this highly motivated group of participants, it has not been necessary to implement procedures to monitor compliance.

Through a process of stratified randomization (according to sex), participants will be randomly assigned to one of 2 study groups. The first group will receive active desensitization , and the second group will not receive any treatment but will be followed up (appendix B protocols) .

The desensitization protocol will be performed at the Center of Innovative medicine (CIM) as is currently done for our milk and peanut desensitization study, under the direct supervision of the medical and nursing staff, and with full cardiopulmonary resuscitation measures available for the treatment of possible allergic reactions that could occur during

the procedure. Oral and intravenous doses of diphenhydramine and intramuscular epinephrine were at the bedside at all times.

Desensitization to egg .⁽¹²⁾

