At the initial visit and at all follow-up visits, participants will be asked to produce 5 ml of saliva. Our work in previous desensitization studies has demonstrated that even children as young as 6 years can produce this volume of saliva. Egg-specific salivary IgA will be determined by ELISA

5. Statistical Considerations

Given that previous studies in adults have attributed at least 50% improvement in the ability to tolerate egg ⁽⁷⁵⁾ with an α of 0.05 and a power ($1 - \beta$) of 0.80, a sample of 17 cases and 17 controls will be recruited. Statistical analyses will be performed using paired t-tests. A P value of <0.05 will be considered significant.

Descriptive statistics of the variables including means, standard deviations and frequencies were computed for all study variables. The concentrations of egg -sIgE and sIgG , the weal size , Mast cell, salivary IgA, T cell and DNA methylation status at the different study time-points will be compared with their baseline values using the one-sample paired t-test and to the control using a 2 sample t-test .

Multiple regression models will be used to assess factors associated with response to desensitization (i.e. baseline demographic characteristics; gender; age; baseline basophile

activation; T cell status, baseline SPT and specific IgE, salivary IgA, and DNA methylation status,).

6. Ethical Considerations

In the consent form given at study enrolment, participants will be advised that they will be randomly assigned to either desensitization treatment or observation alone for one year, (appendix B). Participants will also be advised that their data will be shared only among the study members. Participants who will be at the control group will be told that they will be offered the desensitization protocol one year after study entry.

7. Participant Confidentiality and Record Retention

All participants will be assigned a unique study code that will be used on all study documents. The link between the participants' code and their name will be stored on a password protected computer in the MUHC's Centre for Innovative Medicine, which is a restricted access unit. All study documents will be kept in a locked filing cabinet in the Centre for Innovative Medicine. Only members of the study team, and authorized oversight bodies will be allowed access to the study documents.

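### The plan gives two incompatible randomisation schemes (age and sex, or sex only) with no age bands, and its one explicit between-arm test uses neither the randomisation factors nor the baseline value

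*Combined protocol and SAP*

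**What the plan says.** Section 3.ii (Why Egg), trial-design paragraph: "Patients will be block randomized in groups of 2 according to age and sex". The same paragraph sets the allocation: "The ratio of patients to control is 1:1".

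Section 4, Subject Recruitment and Retention: "Through a process of stratified randomization (according to sex), participants will be randomly assigned to one of 2 study groups". Age and block size are not mentioned here.

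Section 4, opening sentence, gives the population: "Thirty four boys and girls with between 6 to 18 years of age". No age band or cut-point appears anywhere in the document.

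Section 5 (Statistical Considerations) gives the size, "a sample of 17 cases and 17 controls will be recruited", and then says in one general sentence that analyses will use paired t-tests. The next paragraph covers sIgE, sIgG, weal size, mast-cell, salivary IgA, T-cell and methylation measures, which are to be "compared with their baseline values using the one-sample paired t-test and to the control using a 2 sample t-test". Age and gender appear only in the regression on predictors of response, for which no treatment-arm term is stated.

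The primary variable (section 4, Variables measured, item A) has three categories of tolerance at one year. Section 5 names no between-arm test for it.

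**The concern.** Both randomisation statements are current text about the same allocation. A list built from section 4 does nothing to balance age. A list built from section 3.ii cannot be produced as written, because age has no bands.

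Age is a plausible prognostic factor on the document's own account: section 3.ii discusses resolution of egg allergy with age, and section 5 lists age as a candidate predictor. With 17 children per arm, an uncontrolled factor can differ noticeably by chance. If it is controlled at randomisation but left out of the analysis, the standard error is too large for the design. At stake are precision, and an adjustment fixed in advance instead of chosen after an imbalance is seen.

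**Working it through.** **1. The plan's own figure.** 17 per arm at alpha 0.05 (taken as two-sided) and power 0.80 cannot be reproduced from the stated inputs, because no SD is given. With an assumed standardised effect d = 1, the normal formula 2(1.96 + 0.84)²/d² gives 15.7, so 16 per arm. The t-based version gives 16.7, so 17 per arm, with power 0.807. I therefore use d = 1 below. The point does not depend on it.

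**2. Chance imbalance in age.** The document gives no age distribution, so these are assumptions.
- Ages uniform over 6-18: SD = 12/√12 = 3.46 years. SE of the arm difference = 3.46 × √(2/17) = 1.19 years. P(gap of 2 years or more) = 9%.
- SD of 3 years: SE = 3 × √(2/17) = 1.03 years. P = 5%.

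Simulation with 34 children, blocks of 2 and an illustrative age cut at 12:

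| Ages | Scheme | SD of gap (years) | P(>1 year) | P(>2 years) |
|---|---|---|---|---|
| Uniform | Sex only | 1.19 | 40% | 9% |
| Uniform | Sex and age cut | 0.65 | 13% | 0.2% |
| Skewed young | Sex only | 0.89 | 26% | 2.4% |
| Skewed young | Sex and age cut | 0.59 | 9% | 0.1% |

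**3. Effect on the test.** Uniform ages, linear age effect, 6,000 simulated trials per cell. The adjusted analysis is ANCOVA with age and sex.

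| Variance explained by age | Scheme | Type I error, t-test / ANCOVA | Power at d = 1, t-test / ANCOVA |
|---|---|---|---|
| 0% | Sex only | 5.1 / 4.9% | 80.8 / 79.6% |
| 0% | Sex and age | 5.6 / 5.4% | 80.0 / 79.3% |
| 10% | Sex only | 4.7 / 4.9% | 80.6 / 82.8% |
| 10% | Sex and age | 4.0 / 4.7% | 81.5 / 84.4% |
| 25% | Sex only | 4.8 / 5.0% | 79.4 / 89.3% |
| 25% | Sex and age | 3.0 / 4.7% | 82.4 / 89.7% |
| 40% | Sex only | 5.7 / 5.2% | 81.5 / 94.4% |
| 40% | Sex and age | 2.4 / 5.0% | 83.3 / 94.7% |

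The Monte Carlo SE at 5% is √(0.05 × 0.95/6000) = 0.28 points, so 5.6% and 5.7% are not evidence of inflation.

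**4. Cross-check of the conservative error rate.** The age cut reduces the variance of the age gap to (0.65/1.19)² = 0.30 of its sex-only value. If age explains a share R of the variance, the true variance of the arm difference is about (1 − R) + 0.30R of what the t-test assumes. For R = 0.10, 0.25 and 0.40 this is 0.93, 0.825 and 0.72. Dividing the critical value 2.037 (32 df) by the square roots gives 2.11, 2.24 and 2.40, hence type I errors of about 4.3%, 3.2% and 2.2%. These agree with the simulation.

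**5. Baseline value.** Adding it to the marker ANCOVA should gain more precision, but the document gives no correlation between baseline and follow-up, so I put no figure on it.

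**The case against.** Four objections deserve an answer.

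**Chance imbalance is not bias.** A reader might infer that an age gap would confound the treatment effect. The document does not support that. Allocation is random under either scheme, and chance differences are already covered by the test's error rate. This objection stands in full.

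**The age-gap figures do not reach the outcome.** A 9% chance of a two-year gap says nothing by itself about tolerance. Section 3.ii cites 68% resolution by age 16. If 0% to 50% had resolved by age 6 (assumed) and the hazard is constant over the next ten years, yearly resolution is between 1 − (0.32/0.50)^(1/10) = 4% and 1 − 0.32^(1/10) = 11%. Under a constant hazard, an age gap adds no bias by this route. If success were 80% (section 3.ii reports nearly that for milk) against 4-11%, an unadjusted Fisher test with 17 per arm has about 99% power or more. At 70% against 11% it still has 94%. For the primary comparison, then, adjustment mainly keeps the analysis consistent with the design. The clearer gain is for the markers.

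**The matched-pairs reading.** Groups of 2 by age and sex, 17 in each arm, and a general reference to paired t-tests could describe 17 matched pairs. The matching would then enter the analysis. Against this, section 5 next uses the paired test for change from baseline and a separate two-sample test against control. No matching rule is given, and section 4 omits age. The text does not settle it, so the tempting claim that no planned arm comparison uses either factor is not secure.

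**The power gain is assumed.** At 10% of variance explained, adjustment adds about 3 points under age-and-sex stratification. The gain of about 11 points needs 40%. At zero, adjustment costs about 1 point. This stands, and the range should be reported as assumption.

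**Conclusion.** The contradiction between sections 3.ii and 4, and the absence of age bands, rest on the text alone. So does the finding that the only explicit between-arm test, confined to the markers, ignores the randomisation factors and the baseline value. The primary variable has no clearly named between-arm test, and the paired t-test sentence does not say whether it means matched pairs.

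The size is moderate and conditional. With age stratified and explaining 10-40% of outcome variance, the unadjusted test is conservative (type I error about 4.0% down to 2.4%) and has about 82-83% power, against 84-95% with adjustment. With sex-only allocation the unadjusted test keeps its nominal level, but the precision available from age is still unused. If age is not prognostic, little is lost. These figures assume d = 1, uniform ages, a linear age effect and a cut at 12 years. None of them comes from the document.

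A reader might go further and infer false-positive inflation or an invalid trial. Neither follows.

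**What to change.** 1. State one scheme in both sections: either sex plus one predefined age cut (for example 6-11 and 12-18 years), or sex only. If sex-only lists have already been issued, keep them and correct section 3.ii.
2. Analyse each marker by ANCOVA on the follow-up value, with arm, baseline value, sex and age as terms.
3. Name a between-arm comparison of success for the primary variable, stratified by or adjusted for the factors actually used (for example a stratified exact or Mantel-Haenszel test).
4. Say whether the paired t-tests mean change from baseline or matched pairs. If matched pairs, give the matching rule.

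The cost is protocol wording and a slightly longer analysis program. Age, sex and baseline markers are already to be recorded. Four strata with blocks of 2 leave at most four incomplete blocks, so the worst split is 19 to 15. The standard error then rises by a factor of √[(1/19 + 1/15)/(2/17)] = 1.007. With sex only, the worst split is 18 to 16.

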Reactions during the desensitization protocol will be classified according to the categories proposed by Perry et al.⁽⁶⁹⁾: mild reactions are defined when symptoms are limited to the oral mucosa or the skin; severe reactions include cardiovascular or respiratory symptoms or involvement of any four systems; all other reactions will be classified as moderate, although we will consider isolated abdominal discomfort as mild when it lasted for 30 min or less (appendix C protocols).

Build-up phase

Subjects will begin daily home dosing based on the highest dose tolerated during the modified rush of powdered egg white in 1 to 2 tablespoons of baby food or other acceptable vehicle food. Home doses will be provided in individual pre-weighed containers, and subjects will be instructed to ingest 1 dose daily for 2 weeks. As long as

subjects tolerate current doses, the doses will be increased every 2 weeks (see dosing schedule Appendix B) until reaching 150 mg and then increased by 50 mg at each visit until reaching maintenance (300 mg). Dose escalations will be made at visits in the research unit to ensure that subjects tolerate increases, and subjects will be observed for at least 2 hours after increases for signs of clinical reactions. Subjects will be given diaries to track their dose-related symptoms during the study

The protocol will be individualized according to each patient's tolerance to egg:

- Mild allergic reactions will be treated when necessary and the regimen will be continued when the patient becomes asymptomatic. The previously tolerated dose will be repeated before resuming the process.

- Moderate reactions will be treated and desensitization would be restarted on the following day at the previously tolerated dose.

- Severe reactions will be treated with the necessary measures and in the appropriate department, followed by an assessment of whether to interrupt desensitization or reduce the dose on the following day to 1/10 of the dose that caused the reaction.

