The patients' parents will be instructed verbally and in writing about the recommendations to be followed after desensitization and how to treat possible allergic reactions. They will also given a direct telephone line for consultation. Patients will be instructed not to perform physical exercise ^(70;71) for 2 h after eating egg and not to take non-steroidal anti-inflammatory drugs for 3 h before or after ingestion. No special recommendations will be given for viral infections.⁽¹¹⁾ Participants will be given

symptom diaries and instructed to complete it daily to keep track of their allergic symptoms during the desensitization process.

Participants who are not able to achieve desensitization (desensitization defined as being able to tolerate the 300 mg maintenance dose) by 18 months following the initiation of the desensitization process will be considered treatment failures and discontinued from the study.

Maintenance/ Follow-up Phase

Once subjects reached the daily dose of 300 mg, they will be instructed to take this daily for the length of the study (12 months). The subjects will be also instructed to otherwise continue an egg-elimination diet for the duration of the study. Subjects and families will be asked to complete daily home diaries to document that daily doses were taken, as well as to report accidental ingestions, problems with dose administration, or related symptoms. Follow-up visits in addition to and in conjunction with the biweekly visits for dose escalation will be planned at 3, 6, 9, 12 months from the second egg challenge. Each visit will involve a medical history and physical examination. egg specific skin prick testing (SPT), a blood draw similar to that at the challenge to measure serum egg-specific IgE and IgG concentrations, T cell penotyping and DNA methylation. A 5 ml saliva sample will be collected to assess salivary IgA

Food challenges

One month after subjects reach the 300 mg dose, they will undergo a second food challenge to determine his or her allergenic reactivity to egg protein. Subjects will continue OIT dosing through the day before the challenge. The challenge will consist of 10 doses of powdered egg white given every 10 to 20 minutes in increasing amounts up to a total of 8 g of powdered egg white (6 g of egg protein).

After their year in the control arm, , oral desensitization will be offered to the control patients

Variables measured. The following variables will be measured in each patient:

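### Build-up dosing has no clearly described intake record, no check of doses taken before an increase, and no missed-dose rule

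*Combined protocol and SAP*

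**What the plan says.** **Compliance.** Section 4, Subject Recruitment and Retention, reports of a highly motivated group that "it has not been necessary to implement procedures to monitor compliance". No adherence figures accompany the statement.

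**Build-up dosing.** In Section 4, Build-up phase, home doses come in individual pre-weighed containers and children are "instructed to ingest 1 dose daily for 2 weeks". The condition for stepping up is tolerance: provided "subjects tolerate current doses, the doses will be increased every 2 weeks". Increases are given in the research unit, where "subjects will be observed for at least 2 hours after increases for signs of clinical reactions".

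**Build-up diaries.** "Subjects will be given diaries to track their dose-related symptoms during the study". Later in the same phase, participants are to be given "symptom diaries and instructed to complete it daily to keep track of their allergic symptoms during the desensitization process".

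**Maintenance diary.** Under Maintenance/Follow-up Phase, after 300 mg is reached, families keep daily diaries that also show whether each dose was taken. The same paragraph schedules follow-up visits alongside the biweekly escalation visits and says that each visit includes a medical history.

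**Dose adjustments.** After a mild reaction the last tolerated dose is repeated. After a moderate one, dosing restarts the next day at that dose. A severe one leads to an "assessment of whether to interrupt desensitization or reduce the dose on the following day to 1/10 of the dose" that caused it. Appendix B lists actions for families and staff by reaction grade. Parents get spoken and written advice and are "given a direct telephone line for consultation". The topics named are exercise, anti-inflammatory drugs, viral infections (no special advice) and treatment of reactions.

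**The concern.** Tolerating a dose means something only if the dose was taken. The escalation condition does not ask for that, and the diaries described for build-up do not clearly record it. A fortnight without symptoms looks the same whether the child took every dose or only a few.

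Two things are at stake. The first is safety. A child who has been off the dose for some days could be given a higher one, or could go back to the full dose at home, with no described prompt to ask about the gap.

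The second is interpretation. The number and severity of reactions (B.1) and the days until desensitization (B.3) are declared secondary variables, and children who do not reach 300 mg by 18 months are classed as treatment failures. Without a clear intake record, a reader could not readily tell a reaction on regular dosing from one on resumption after a gap.

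**Working it through.** No planned figure depends on this point, so the check is mainly a comparison of texts.

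**1. What each phase describes (Section 4 and Appendix B)**

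| Item | Build-up | Maintenance |
|---|---|---|
| Home dosing | Daily, two weeks per level | Daily, 300 mg |
| Diary content | Symptoms | Doses taken, accidental ingestions, dosing problems, symptoms |
| Condition for an increase | Current dose tolerated | Not applicable |
| Check of doses taken before an increase | None described | Not applicable |
| Trigger for adjustment | Reaction, by grade | Reaction, by grade |
| Rule after missed days | None described | None described |

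**2. One child followed through the rules.** Take a child on 50 mg who misses several consecutive days and reports no symptoms. None of the mild, moderate or severe rules applies, because there was no reaction. At the two-week visit the tolerance condition is met on its face, and the next level, 75 mg, is given under observation. If the child resumes before the visit, the next container holds the full 50 mg and is taken at home. No visible instruction tells the family to call first.

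**3. The protocol's own rationale.** Section 3.iii defines desensitization as a state that depends on continued regular exposure. Section 3.ii cites evidence that avoidance lowers the threshold for later reactions. Section 3.iii also mentions possible loss within 48 hours of stopping, but calls that evidence flawed (3 patients). On the protocol's reasoning, a gap is a plausible contributor to a reaction on resumption.

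**4. Length of the period concerned.** Appendix B lists 17 levels, with 300 mg as level 17. Assume that build-up follows this list in two-week steps with no repeats:

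- escalations = 17 − starting level
- weeks = 2 × escalations
- home doses = 13 or 14 × escalations, depending on whether the first dose of each block is the one given in the unit

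| Starting dose (level) | Escalations | Weeks | Home doses |
|---|---|---|---|
| 0.1 mg (1) | 16 | 32 | 208 to 224 |
| 25 mg (9) | 8 | 16 | 104 to 112 |
| 100 mg (12) | 5 | 10 | 65 to 70 |
| 300 mg (17) | 0 | 0 | 0 |

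These are doses for which no record is clearly described. They are not estimates of doses missed. If the dose-taken diary is meant to start at the first home dose, all of them are covered.

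**5. Which results are touched.** B.1 and B.3 can be calculated without intake, but would lack it as context. Under the written rules, a gap with no reaction changes no dose and adds no days to B.3. A gap matters for B.3 only through a reaction. Putting a number on that needs a missed-dose rate and the chance of a reaction after a gap, and the documents give neither. The primary variable (tolerance at 1 year) and the Section 5 regression, whose listed factors are baseline ones, do not use intake.

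**The case against.** The strongest reply is that the record may already exist. The dose-taken diary sits in a paragraph that also mentions the biweekly escalation visits, which belong to build-up. Its start date is therefore ambiguous, and the gap may be one of drafting. This limits the point to a record that is not clearly described. The placement under Maintenance, after 300 mg is reached, still favours the narrower reading.

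Other replies also carry weight. The compliance sentence describes past experience and does not cancel the maintenance diary. Visits include a medical history, at which missed doses could come up, although no such question is specified. The written advice to families is not in the documents, and Appendix D shows no schema content, so only absence from the visible text is shown. Increases are observed, caregivers hold epinephrine and are taught to use it, and there is a telephone line. Section 3.iii also cites trials in which a maintenance dose at least twice a week was enough to avoid reactions, so short gaps may be harmless. That evidence concerns maintenance, however, and the same part of the protocol lists the required frequency as unknown.

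What stands is that observation tests the new dose, not the home doses before it, and that resuming at home after a gap is the less protected event.

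A reader might infer that the trial records no intake at all. The maintenance diary contradicts that. A reader might also infer that build-up intake would be lost for good. The documents do not support this either, because daily symptom diaries, pre-weighed containers and visit histories could give indirect information.

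**Conclusion.** The point holds for build-up. The plan bases escalation on tolerance alone, clearly describes a dose-taken record only for maintenance, and describes no missed-dose rule. As written, a child with missed doses and no symptoms could be escalated, or could resume the full dose at home. B.1 and B.3 would have no clearly described intake record beside them.

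No size can be given, because the documents state no missed-dose rate. It would be tempting to put a number of extra days on B.3 from the reaction rules. Such a number would measure the cost of a reaction, whatever its cause, and not the cost of missed doses. It would be equally tempting to conclude that the primary result is biased. The documents do not support that: missed doses are part of the strategy as delivered, and the comparison of the randomised groups does not use intake.

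The conclusion assumes that the unseen written instructions contain no missed-dose rule and that the dose-taken diary starts where its heading places it. If both assumptions are wrong, what remains is the lack of a described check before each increase. The change is worth making before enrolment because it is cheap and safer.

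**What to change.** - Replace the compliance sentence in Subject Recruitment and Retention with a statement that intake is recorded from the first home dose.
- State under Build-up phase that the dose-taken diary in Maintenance/Follow-up starts at that dose.
- At each planned two-week visit, review the diary and count returned pre-weighed containers before any increase.
- Add a missed-dose rule. After a number of consecutive missed days, set by the clinical team before enrolment, the family calls the study line before dosing, and the next dose is repeated or reduced under observation in the CIM. Put the same rule in the families' written instructions.
- Report doses taken descriptively alongside reactions and treatment failures. Leave the primary comparison as it is.

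The cost is one diary field from an earlier date, slightly longer visits that are already planned, and an occasional extra observed dose. No extra patients are needed. Intake would still be self-reported or counted, not proven.
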